9.0 Study Withdrawal/Discontinuation

Patients may withdraw consent at any time during the study participation without bias or alteration in their ongoing cancer care. The reason for discontinuation or withdrawal will be documented in the study record.

The investigators reserve the right to take patients off of study for failure to comply with study parameters, if patients have undue toxicity secondary to gabapentin, or if the investigators feel it is in the best interest of the patient.

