2.0 Specific Aims

Specific Aim 1: To determine whether Gabapentin used as a preventive measure during chemoradiation can reduce radiation-induced mucositis associated pain in head and neck cancer patients as measured by: 1) pain scores on the Vanderbilt Head and Neck Symptom Survey (VHNSS version 2.), and 2) analgesic use.

Hypothesis 1.1: Compared to controls, patients using Gabapentin during radiation-based therapy will have a 1.5 point decreases in self-reported oropharyngeal pain (on a scale of 0 to 10) week six of radiation.

Hypothesis 1.2: Compared to controls, patients using Gabapentin during radiation-based therapy will have a 20% decrease in opioid use (as measured in morphine equivalents) at week six of radiation.

Specific Aim 2: To determine whether pain control is associated with weight loss (in pounds) and duration of use of percutaneous endoscopic gastrostomy utilization (in days).

Hypothesis 2.1 Patients with less pain will have decrease weight loss.

Hypothesis 2.2 Patients with less pain will have a shorter duration of PEG placement.

Specific Aim 3: To assess the safety (grade 3 or 4 adverse events) and tolerability of using gabapentin (discontinuation of drug due to side effects - yes or no).

Specific Aim 4: To correlate pain severity with frequency and severity of general systemic symptoms.

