5.0 Study Procedures

5.1 Chemoradiation:

Chemotherapy and radiation will be instituted per standard of care. There will be no alterations in standard of care as a result of participation in this study. Disease treatment related data will be obtained through chart review after the completion of therapy.

5.2 Study Treatment:

Patients will be randomized to Arm 1 (Usual Care) or Arm 2 – (Usual Care plus Gabapentin).

Arm 1: Usual Care:

Usual care will include the following:

1. Oral health measures including brushing, flossing, and the use of fluoride toothpaste
2. Oral rinsing with baking soda and salt water gargles every 2-3 hours while awake
3. Miracle mouthwash formulated to include topical lidocaine, Benadryl, and Maalox;
4. Nonsteroidal anti-inflammatories around the clock to treat pain and inflammation
5. Opioid analgesics to include a fixed and breakthrough medication.

Patients will undergo an education session at the beginning of treatment to review foundations of oral care and pain management.

Arm 2: Usual Care plus Gabapentin.

Patients will receive all measures for Arm 1 **PLUS** Gabapentin. Gabapentin will be dose escalated using a slow escalation schema to minimize the sedating effects of medication and avoid undue toxicities:

- Week 1: Gabapentin 100 mg PO 3 times a day
- Week 2: Gabapentin 300 mg PO 3 times a day.
- Week 3: Gabapentin 600 mg PO 3 times a day.
- Week 4 onward: Gabapentin 900 mg PO 3 times a day.

The highest tolerated dose of gabapentin will continue throughout treatment. Missed doses, though regrettable, are part of any patient-administered medication and will not be considered deviations for this study as we are studying practical efficacy. After completion of therapy, mucositis is expected to resolve at a variable rate (1 to 3 months post treatment). Gabapentin will be continued until mucositis resolves **and** pain subsides. Patients will be weaned off opioids prior to initiation of gabapentin de-escalation. Once opioids have been weaned, de-escalation of gabapentin will be initiated. Since the rate at which patients can be weaned of pain medications is variable, de-escalation will be managed by the treating physician. Abrupt discontinuation of gabapentin will be discouraged in order to avoid symptoms related to withdrawal.

5.3 Dose Modifications:

Prior to each dose escalation, patients will be assessed for side effects related to gabapentin.

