- Patients who are tolerating the current dosing schedule will undertake an escalation to the next dose level.
- If patients have mild to moderate side effects related to gabapentin, no further dose escalation will be undertaken
- If patients develop severe side effects attributable to gabapentin, gabapentin will be held until the side effects have totally resolved and then restarted at the last known tolerated dose level.
- Although rare, severe mood alterations and suicidal thoughts have been associated with this agent. Should patients experience these symptoms, gabapentin will be permanently discontinued.

5.4 Route of Administration:

Gabapentin is usually taken orally. Gabapentin may also be crushed and given via feeding tube if the patient is unable to swallow the tablet.

5.5 Pain Management:

Pain management for tumor and treatment related toxicities will be at the discretion of the treating physician. Opioid and adjuvant use will be documented for study purposes. At the completion of study, patients on Arm 1 may be started on gabapentin if they have uncontrolled mucositis associated pain. For patients assigned to Arm 1, the treating physician will manage the utilization of gabapentin during the post-treatment phase

5.6 Study Visits:

In order to minimize inconvenience to patients under study, study visits will coincide with scheduled treatment. This may introduce a degree of variability in the timing of weekly visits and follow-up visits which will be considered acceptable except in cases where explicit visit timing is dictated elsewhere in the protocol. Weekly on treatment visits that are more than 1 week late will be considered missing.

Baseline:

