Study Visit: The study nurse will meet with the patient at baseline, weekly during radiation therapy, and at 1, 2 and 3 months post-treatment. At each study visit the study nurse will 1) administer appropriate questionnaires, 2) review the patient's pain diary and compliance diary, 3) document concurrent medications, 4) document toxicities based on CT CAE criteria 4.0, 5) identify and prepare reports for any adverse events, 6) document any dose adjustments in pain medications as recommended by the physician or nurse practitioner, and 7) educate the patient regarding medication dose and schedule.

As these patient reported outcome measures represent outcomes of interest for the study, they will not be altered by study staff due to missingness as changes would threaten the validity of the tool.

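### Section 9.0 lets investigators take patients off study for non-compliance or gabapentin toxicity, and nothing expressly provides for collecting their outcomes afterwards

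*Combined protocol and SAP*

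**What the plan says.** Section 9.0 gives investigators a discretionary right to "take patients off of study for failure to comply with study parameters, if patients have undue toxicity secondary to gabapentin". A third ground is the investigators' own view of what serves the patient best. The one follow-through it states is "The reason for discontinuation or withdrawal will be documented in the study record".

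Other sections deal with the same kinds of event without study exit:

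- **Section 5.3 (dose modifications).** For severe side effects, "gabapentin will be held until the side effects have totally resolved and then restarted at the last known tolerated dose level". For severe mood changes or suicidal thoughts, "gabapentin will be permanently discontinued". Neither rule mentions leaving the study.
- **Section 2.0, Aim 3.** Tolerability is an outcome, defined as "discontinuation of drug due to side effects - yes or no".
- **Section 5.2.** Missed doses "will not be considered deviations for this study as we are studying practical efficacy".
- **Appendix D.** The compliance diary has a branch for a patient who is not taking gabapentin, who skips only the rest of that diary.

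Section 6.2 schedules study visits at baseline, "weekly during radiation therapy, and at 1, 2 and 3 months post-treatment". Section 10.0 applies intent-to-treat to all analyses, expects loss to follow-up to be non-random, allows for up to 30 losses among 150 randomised, and cites a published strategy for handling missing outcomes.

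**The concern.** An intent-to-treat comparison needs outcomes for the patients in each randomised arm, including those who stop or misuse the drug. Section 9.0 lets an investigator end participation because of what happened on the drug, and says nothing about pain scores, opioid use, weight or feeding-tube data from then on.

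The toxicity ground is one-sided. While treatment lasts, only Arm 2 receives gabapentin under the protocol, and the comparator is usual care without placebo. The compliance ground can apply to either arm, but what counts as compliance with study parameters is not defined. If patients removed from Arm 2 differ in pain from those who stay, and Arm 1 has no matching removals, the arms are no longer comparable at week six or later. This loss comes from the rule and not from the patient's own decision, so much of it could be prevented.

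**Working it through.** **Step 1: what happens to the data.**

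| Event | Drug | Study participation | Outcomes afterwards |
|---|---|---|---|
| Severe side effect (5.3) | held, later restarted | not mentioned | visits as scheduled |
| Mood change or suicidal thoughts (5.3) | stopped for good | not mentioned | visits as scheduled |
| Missed doses (5.2) | not a deviation | not mentioned | visits as scheduled |
| Undue toxicity (9.0) | not stated | may be ended | not stated |
| Failure to comply (9.0) | not stated | may be ended | not stated |

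For the first three rows, the last column is inferred from the absence of any exit rule. The chart review in section 5.1 does not fill the gap in the last two rows, because it covers disease-treatment data only.

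**Step 2: the plan's own loss figure.** 120 / (1 − 0.20) = 150, which agrees with section 10.0. The allowance covers all losses. It is not an estimate of removals under section 9.0, for which the documents give no figure.

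**Step 3: illustration.** From section 10.0: SD 2.8, 60 analysed per arm, target difference 1.5 points. Assumed: a fraction f of Arm 2 is removed, their unseen week-six pain is d points above that of the patients retained, Arm 1 has no such removals, and the analysis uses complete cases.

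- Standard error = 2.8 × √(2/60) = 0.511.
- Bias in favour of gabapentin = f × d.
- Two-sided type I error = P(|Z + bias/0.511| > 1.96).

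| f | d | Bias | Share of 1.5 | Type I error |
|---|---|---|---|---|
| 5% | 1 | 0.05 | 3% | 5.1% |
| 10% | 2 | 0.20 | 13% | 6.8% |

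For the second row, bias/SE = 0.20/0.511 = 0.39. If d is negative, the bias runs against gabapentin.

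**Step 4: keeping earlier scores.** The 10%, 2-point case was simulated with no treatment effect, 75 randomised per arm, about 60 per arm with a week-six score, and one earlier score retained for everyone (assumed correlation with week six 0.5 or 0.7). If half or all of the excess already shows in the earlier score, type I error is about 5–6%. If none shows, it is about 7%, so nothing is gained.

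**Step 5: balanced removal.** With the same fraction and the same excess removed from both arms, the bias cancels and type I error is about 5%.

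**The case against.** The strongest reply is that section 9.0 is a residual discretion. The operative toxicity rules are in 5.3, and none of them requires study exit. Aim 3 and Appendix D presuppose patients who stop the drug and stay in the study. Section 5.2 can be read as narrowing the compliance ground, and what is left of that ground may be missed visits and forms, whose data were hard to obtain anyway. Section 10.0 plans an investigation of missing-data patterns and commits to a cited strategy. Much of this stands: it makes frequent use of the clause less likely and limits the harm. It does not close the gap. Neither 5.2 nor 5.3 limits section 9.0, and section 10.0 speaks of handling missing outcomes without stating that they are collected after removal. What the cited strategy requires is not set out in the documents.

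A reader might infer that section 9.0 contradicts intent-to-treat. The documents do not support that, because removal is discretionary and nothing says that removed patients or their data are excluded from analysis.

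A reader might also infer serious inflation of type I error. With f = 20% and d = 2.8 the formula does give a bias of 0.56 and 19.5%. That case charges the whole of Arm 2's loss allowance to this one clause and makes the removed patients a full SD worse. Nothing in the documents supports either input.

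**Conclusion.** The point holds as a gap that should be fixed, with medium confidence. Section 9.0 permits investigator-initiated exit on grounds tied to gabapentin, no section expressly provides for outcomes afterwards, and the toxicity ground during treatment falls on one arm only. The rule therefore weakens the data behind the stated intent-to-treat analysis without contradicting it.

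How much it matters in practice cannot be derived from the documents. The figures above rest on assumed removal rates and pain differences, complete-case analysis unless stated, and loss confined to Arm 2. They run from negligible to a modest distortion, and the direction would reverse if removed patients would have had less pain. The case for acting is that the loss is preventable at low cost, not that a large bias has been shown.

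**What to change.** In section 9.0, state that:

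1. Stopping gabapentin does not by itself end study participation.
2. After any investigator-initiated removal, on whatever ground, the scheduled weekly, end-of-treatment and 1, 2 and 3 month outcome assessments continue, unless the patient withdraws consent to follow-up or the investigator judges that the assessments themselves are not in the patient's interest.

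The second statement has to cover all three grounds. If the best-interest ground were left without follow-up, a patient with toxicity could still leave by that route with no outcomes recorded.

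Reconcile section 9.0 with the missed-dose statement in 5.2 and the toxicity handling in 5.3, without changing any drug-handling rule. Tabulate exits by arm, time and ground.

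The cost is a few sentences and a little follow-up effort at visits already scheduled. The tabulation needs little new, since reasons for exit are already recorded. Some loss through withdrawn consent will remain.

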10.0 Statistical Considerations and Sample Size Justification

General evaluation and analysis plan: Statistical software will be used to summarize the data collected and to test study hypotheses. Intent-to-treat principles will be used for all analyses. An interim analysis of the VHNSS pain scores will be conducted when 50% of the participants have been randomized and have completed the 3 month follow-up period. To maintain the final overall alpha of $P < 0.05$, the Haybittle-Peto approach will be used: the trial will be stopped at that point if the symmetric stopping boundaries of $P < 0.001$ are met. The interim analysis will only be used for this purpose, i.e. no futility analyses will be conducted.

Management of Missing Data: In-depth investigations of patterns of missing data will be undertaken. Given the longitudinal nature of this study, we expect two types of missing data: 1) randomly missing responses to items within the self-report measures (e.g., VHNSS) and 2) non-randomly missing lost-to-follow up (LTF) assessments. Our proposed sample size accommodates up to 30 LTF (i.e., up to 20% of those randomized) to arrive at a total analysis sample size of 120. Randomly missing item response data will be handled via protocols specified by the instrument developers. When there is no specified protocol, if the participant has completed 75% or more of the items on a particular instrument, prorated scores for that instrument will be generated using available item responses. Non-randomly missing data will be assessed to determine whether it provides clinically important information and implications for generalizability of findings. All efforts as outlined by White et al. (2011) for handling missing outcome data in an RCT-ITT analysis will be conducted.

Analyses for study aims. Graphical and descriptive statistical summaries will be generated for all study variables. Evaluation of the key outcome variable data distributions (VHNSS mouth pain scores, opioid dose) will inform the required test distribution (e.g., normal, log-normal). Mixed-level general linear modeling will be used to test study hypotheses. Given that patients will have varying VHNSS pain scores prior to beginning radiation, those baseline values will be included as a covariate in the analyses of outcomes [EOT: VHNSS pain scores (H1.1); opioid use (H1.2); weight loss (H2.1); duration of PEG (H2.2); general symptoms (Aim 4)]. Frequency distributions will summarize the safety and tolerability outcomes (Aim 3). All tests of statistical significance will maintain maximum Type I error of 0.05 ($p < 0.05$).

Sample size justification. The proposed sample size was based on typical VHNSS pain score values during/end-of-treatment in prior studies (M=4.5, SD=2.8). A total sample size of 120 patients (60 per arm) who complete the protocol will provide 80% statistical power (2-tailed alpha=0.05) to detect a decrease of 1.5 points on the VHNSS pain scale due to the addition of gabapentin to usual care. Given a change of 2.0 points on the scale is proposed to be clinically meaningful, this slightly larger sample size will provide coverage in the case that our sample values are slightly more variable than those observed in our prior studies. A total sample size of 120 will also enable us to detect correlations as small 0.25(6.3% shared variance) with 80% power and 2-tailed alpha=0.05. We expect clinically meaningful associations to be larger than this value.

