Prior to initiating therapy, patients will undergo education sessions with study staff. The educational intervention will include a discussion of oral health foundations as well as a discussion of pain management. This education is standardly applied to all VUMC patients undergoing radiation therapy for HNC and will not be otherwise documented. In addition, patients will also be given written material to review. Patient will be given a pain diary and instructed on its use. Baseline pain medication use will be documented. Patients will complete the demographic survey. Patients randomized to gabapentin will be given a prescription for gabapentin with dose escalation as noted in the treatment section. Patients who do not have insurance or who are unable to afford gabapentin will be provided with medication from the indigent pharmacy. All baseline assessments must be done within 4 weeks of starting concurrent chemoradiation.

Weekly On Treatment Visits:

Starting with the initiation of concurrent chemoradiation, patients will be evaluated on a weekly basis. The evaluation will include:

- 1) review of the weekly pain survey
- 2) for patients on gabapentin (Arm 2) --we will review their compliance log and identify any barriers to compliance and strategies to improve their compliance
- 3) adjustment of pain regimen
- 4) completion and review of the Vanderbilt head and neck symptom survey
- 5) mucositis grading.

End-of-Treatment Visit:

Patients will undergo an evaluation at their final radiotherapy visit or within 2 weeks after. This will include the following:

- 1) review of the monthly diary survey
- 2) for patients on gabapentin (Arm 2) --we will review their compliance log and identify any barriers to compliance and strategies to improve their compliance

- 3) adjustment of pain regimen
- 4) completion and review of the Vanderbilt head and neck symptom survey
- 5) mucositis grading.

6.0 Study Measures:

6.1 Mucositis Grading:

Patients will have an oral exam twice a week as part of standard of care. Mucositis will be graded based on the World Health Organization criteria. Mucositis assessments will be done by trained study staff.

6.2 Patient Reported Outcome Measures:

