Appendix I: Studies to be Done:

	Baseline¥	Week 1	Week 2	Week 3	Week 4	Week 5	Week 6 *	Week 7 *	1,2 3 Months post tx
Study Visit	X	X	X	X	X	X	X	X	X
Chemoradiation Teaching	X								
Foundations of Oral Care	X								
Foundations of Pain Management	X								
Randomization	X								
Gabapentin Arm 2 Only		X	X	X	X	X	X	X	X
Mucositis Grading	X	X	X	X	X	X	X	X	X
Demographic Survey	X								
VHNS Version 2.0		X	X	X	X	X	X	X	X
Pain Survey		X	X	X	X	X	X	X	X
Compliance Survey Arm 2 Only		X	X	X	X	X	X	X	X
Neurotoxicity Scale	X						X		X (month 3 only)
POMS	X						X		X (month 3 only)
QOL	X						X		X (month 3 only)

Disease and Treatment Form	X								
----------------------------	---	--	--	--	--	--	--	--	--

‡ All baseline assessments must be done within 4 weeks before starting concurrent chemoradiation.

* Weekly assessments will continue until the completion of chemoradiation which may vary between 5 and 7 weeks.

An End of Treatment Visit will be conducted 2 weeks after Chemoradiation therapy

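### Intent-to-treat covers Aim 3 without exception, so Arm 2 patients who never take gabapentin stay in the denominator of the tolerability rate and lower it

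*Combined protocol and SAP*

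**What the plan says.** Section 10.0 sets the analysis population for the whole trial: "Intent-to-treat principles will be used for all analyses".

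Aim 3 (section 2.0) has two parts. The first is safety: "To assess the safety (grade 3 or 4 adverse events". The second is "tolerability of using gabapentin (discontinuation of drug due to side effects - yes or no". Section 10.0 gives Aim 3 one line of analysis: "Frequency distributions will summarize the safety and tolerability outcomes (Aim 3". It names no denominator, minimum exposure, event window or coding rule for patients who never start, and none appears elsewhere.

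The drug is supplied by prescription (section 5.6, Baseline): "Patients randomized to gabapentin will be given a prescription for gabapentin with dose escalation as noted in the treatment section". Section 5.2 adds that missed doses are not deviations. In Appendix I, randomization is marked at baseline and gabapentin from Week 1.

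Toxicities are graded at every study visit. On visit timing, section 6.2 says: "The study nurse will meet with the patient at baseline, weekly during radiation therapy, and at 1, 2 and 3 months post-treatment".

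**The concern.** Intent-to-treat suits Aim 1, which compares two treatment policies. Aim 3 asks a different question, how well patients who use gabapentin tolerate it, and only people who have taken the drug can answer that.

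Because the drug has to be obtained on prescription after randomization, some Arm 2 patients may never take a dose. With an all-randomized denominator and a yes/no outcome, each such patient adds one to the denominator and nothing to the numerator. On this item the error runs one way only: gabapentin looks better tolerated than it was among those who took it. The choice of denominator sets the headline figure of a stated aim, so it should be settled before results are seen.

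**Working it through.** **Inputs.** From the documents: 150 patients recruited (section 4.0); up to 30 lost, leaving 120 analysed, 60 per arm (section 10.0). Assumed: 1:1 allocation, because section 4.0 describes permuted blocks without a ratio; the share of Arm 2 that never starts; and the share of starters who stop for side effects.

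**The plan's own figure.** 120 / (1 − 0.20) = 150, which reproduces the recruitment target. With 1:1 allocation, Arm 2 has 150 / 2 = 75 patients. The plan states no expected tolerability rate, so there is none to reproduce.

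**Formula.** Let p be the rate of stopping for side effects among starters and s the share of Arm 2 that never starts. Then

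rate over all randomized = [p × 75 × (1 − s) + 0 × 75 × s] / 75 = p × (1 − s).

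| Rate among starters | s = 0 | s = 5% | s = 10% | s = 20% |
|---|---|---|---|---|
| 10% | 10.0% | 9.5% | 9.0% | 8.0% |
| 20% | 20.0% | 19.0% | 18.0% | 16.0% |
| 30% | 30.0% | 28.5% | 27.0% | 24.0% |

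**In whole patients.** With 4, 8 or 15 never-starters among 75 and p = 20%:

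- 0.20 × 71 / 75 = 18.9%
- 0.20 × 67 / 75 = 17.9%
- 0.20 × 60 / 75 = 16.0%

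**Can the planned forms separate the groups?** Only in part. The first question of the compliance diary (Appendix D) asks whether the patient is taking gabapentin, and a no ends the form. A run of weekly answers that opens with yes identifies a starter. A patient whose first answer is no may never have started, or may have taken some doses and stopped because of side effects. The diary does not distinguish these two, and none of the forms shown has a first-dose date.

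**The case against.** The strongest reply is that the plan nowhere says never-starters count as having tolerated the drug. Aim 3 speaks of using gabapentin, and the item cannot apply to Arm 1, so an analyst might restrict it to users without being told. That reading is reasonable, and the coding is indeed unstated. But the only population rule in the plan covers every analysis, and an analyst who follows it gets the diluted rate.

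The second reply is size. At 5% to 10% never-starting, the shift is 1 to 2 points on a rate of 20%. The standard error of that rate with 75 patients is √(0.20 × 0.80 / 75) = 4.6 points. The summary is descriptive and carries no test. Non-starting may also be rare: section 5.6 provides the drug to patients who cannot afford it. All of this stands and keeps the point modest. The shift is nevertheless systematic, and a larger sample would not remove it.

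The third reply is that a safety table by randomized arm is legitimate in a trial that says it studies practical efficacy (section 5.2). That also stands. What is lacking is an exposed-patient summary beside it.

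A reader might infer three stronger things that the documents do not support:

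- *That intent-to-treat charges events before the first dose to gabapentin.* It fixes the arm a patient belongs to, not the window in which events count. The window is simply undefined. Appendix I allows a gap before treatment ("All baseline assessments must be done within 4 weeks before starting concurrent chemoradiation"), but that gap exists in both arms and does not by itself bias the comparison.
- *That gabapentin use in Arm 1 blurs the safety comparison throughout.* Current users are excluded at entry (section 3.0). Section 5.5 foresees Arm 1 use only at completion of study, in the post-treatment phase, so overlap would fall mainly at the visits 1 to 3 months after treatment.
- *That every Aim 3 result is pulled towards good tolerability.* Only the discontinuation item moves in that direction. Pre-dose events counted in Arm 2 would make gabapentin look worse.

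**Conclusion.** The point holds for the tolerability rate. As written, the intent-to-treat rule keeps Arm 2 patients who never took gabapentin in the denominator of an item on which they can only score no, and the rate falls by the factor (1 − never-start share). Across the assumed range of 5% to 20% never starting, a rate of 20% among starters reads as 19% down to 16%, and 30% reads as 28.5% down to 24%.

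The direction follows from the rule and the binary item. The size cannot be known in advance, because the documents give neither a never-start share nor a discontinuation rate. If every Arm 2 patient takes a dose, there is no effect. For grade 3-4 events the finding is narrower: the counting window is undefined and no exposed-patient table is planned, but no bias between the arms follows from that alone. The Aim 1 comparison, the sample size, power and alpha are unaffected. The change should be made, but it does not threaten the trial.

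**What to change.** In section 10.0, limit the blanket sentence to Aims 1, 2 and 4, and add rules for Aim 3:

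- **Tolerability:** report the share stopping for side effects among Arm 2 patients who took at least one dose. Show never-starters on a separate line, with their number.
- **Grade 3-4 events:** count from the start of radiation in both arms. Compare Arm 2 patients who took at least one dose with all randomized Arm 1 patients.
- **Arm 1 patients who later take gabapentin:** show events after that start separately, and do not exclude these patients. Dropping them would select the control group on a choice made after randomization, and section 5.5 ties that choice to uncontrolled pain.
- **Randomized-arm table:** it may be kept beside the exposed-patient table. It is the version that preserves randomization.
- **Data:** record the first-dose date, or that the drug was never started, at whichever weekly visit it becomes known, so that late starters are not missed.

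The cost is a few sentences and one data field, a slightly less favourable discontinuation rate, and a little precision. With 8 never-starters the denominator falls from 75 to 67, and the standard error of a 20% rate rises from 4.6 to √(0.20 × 0.80 / 67) = 4.9 points.

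### The observed data choose the analysis scale for pain and opioid dose, with no rule for zeros, pooling or timing; a log scale would not match the 1.5-point hypothesis for pain

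*Combined protocol and SAP*

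**What the plan says.** Section 10.0, under the analyses for the study aims, starts from "Evaluation of the key outcome variable data distributions (VHNSS mouth pain scores, opioid dose") and says that this evaluation "will inform the required test distribution (e.g., normal, log-normal"). It then states that "Mixed-level general linear modeling will be used to test study hypotheses" and that "All tests of statistical significance will maintain maximum Type I error of 0.05". No transformation, link function, treatment of zeros, selection rule or date for the evaluation is given. Baseline VHNSS pain is the only covariate listed, for the opioid outcome as well.

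The hypotheses in Section 2.0 are on fixed scales. Hypothesis 1.1 is that gabapentin patients will "have a 1.5 point decreases in self-reported oropharyngeal pain", an absolute difference. Hypothesis 1.2 is a "20% decrease in opioid use (as measured in morphine equivalents) at week six of radiation", a relative one. The sample size in Section 10.0 is for the 1.5-point difference: 60 per arm "will provide 80% statistical power (2-tailed alpha=0.05"). No variance, share of non-users or power is given for opioid dose.

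Section 5.6 says of the baseline visit: "Baseline pain medication use will be documented".

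**The concern.** Zero is a possible value of both outcomes. VHNSS subscales start at 0 (Section 6.2, Appendix B description). Item 27 of the form has a box for patients on no pain medication, and Section 5.5 leaves pain treatment to the treating physician. The logarithm of zero is undefined, so a log-normal analysis must either leave those patients out or add a constant, and the plan mentions neither.

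Three things are at stake:

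- **Pain:** moving to logs replaces the difference in points, for which the trial was sized, by a ratio.
- **Opioid dose:** leaving out non-users selects patients on something that happens after randomisation. It also hides one route by which gabapentin could work, namely patients who never need an opioid.
- **Type I error:** without a stated rule, a reader cannot rule out that the scale was picked after the arms had been compared. The interim analysis compares VHNSS pain between arms halfway through, so by the end that comparison will have been seen.

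**Working it through.** **The plan's own figure.** Inputs from Section 10.0: difference 1.5, SD 2.8, two-sided alpha 0.05, power 80%. n per arm = 2 × (1.960 + 0.842)² × 2.8² / 1.5² = 54.7, so 55 (56 with the t distribution). With 60 per arm, power is Φ(1.5 / (2.8 × √(2/60)) − 1.960) = Φ(0.974) = 83.5% (82.9% with t). The stated 80% is therefore slightly conservative, and it holds only for a difference in points on the raw scale.

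**Pain.** Assumption: scores are normal with the plan's mean and SD, rounded and clipped to 0-10. The share of zeros is Φ((0.5 − 4.5)/2.8) = 7.7% under usual care, and Φ((0.5 − 3.0)/2.8) = 18.6% when the mean is 1.5 lower. Clipping shrinks the observed difference to about 1.34. Simulated power with 60 per arm:

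| Analysis of pain | Power |
|---|---|
| raw scale | 81-83% |
| log of positive scores only | 54-56% |
| log(score + 1) | 79% |

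**Opioid dose.** Assumptions, none of them in the documents: log-normal doses among users, log-SD 0.6 / 0.8 / 1.0, and the zero shares shown. Each effect row is a true 20% fall in mean dose. With more non-users and equal doses among users, 0.72/0.90 = 0.64/0.80 = 0.80. Simulated rejection rates with 60 per arm:

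| Source of the 20% fall | Zeros (control, gabapentin) | Raw scale | Log of positive doses |
|---|---|---|---|
| all from more non-users | 10%, 28% | 30 / 20 / 14% | 5 / 5 / 5% |
| all from more non-users | 20%, 36% | 25 / 18 / 14% | 5 / 5 / 5% |
| half and half | not the same in both arms | 32 / 21 / 14% | 15 / 11 / 9% |
| all from lower dose in users | 10%, 10% | 35 / 22 / 14% | 49 / 30 / 21% |

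A ratio of means that keeps zeros (log link, robust variance, unadjusted), at log-SD 0.8, rejects in 18-19% of trials with zeros of 20% and 36%. With 10% zeros in each arm and the whole fall among users, it rejects in 24%, against 29-30% on logs of positive doses.

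**Adding a constant.** At log-SD 0.6 with 10% zeros in each arm and the fall among users, power is 9% with +0.1, 13% with +1 and 24% with +10, against 49% on positive doses alone. When the fall comes from more non-users (10% to 28%), the same constants give 72%, 69% and 59%. An unstated constant therefore decides which kind of effect the test can see.

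**Power for Hypothesis 1.2 in general.** With no zeros, 80% power with 60 per arm needs a log-SD of at most |ln 0.8| / (2.802 × √(2/60)) = 0.436. On the raw scale it needs a coefficient of variation of at most 0.20 / (2.802 × √(2/60)) = 0.39. At log-SD 0.5 / 0.6 / 0.8 / 1.0, power is 69 / 53 / 33 / 23%.

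**Type I error.** If the better of the raw and log-positive results is reported, the opioid false-positive rate is 7-8%. With log(x + 1) as a third option it is 10-11% for opioid dose and 9% for pain. If the scale is picked from pooled data only, it is 4.7-5.5%, which is no inflation.

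**The case against.** The plan does not adopt log-normal. It is one of two examples, and data with many zeros would themselves argue against it. Section 10.0 applies intent-to-treat principles to every analysis, and excluding randomised patients because their recorded dose is zero would breach that. A reader might infer that non-users will be discarded, but the documents do not say so. This stands: the gap is the missing rule.

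Non-users may also be few at week six. Section 5.2 lists fixed and breakthrough opioids in the usual care that both arms receive, and Section 1.2 says pain peaks at the end of therapy. A subscale mean is zero only if every item is zero, so exact zeros for pain may be rarer than the rounded single score used here suggests. This stands too, and it is why the figures are ranges under assumptions. Zeros remain possible, and a log analysis of pain would answer a different question from Hypothesis 1.1 even without any.

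A reader might also infer that the significance tests are invalid. The documents do not support that. They do not say that the inspection is by arm, nor that the more favourable result will be reported, and a pooled choice leaves the error rate at about 5%. Equally, they do not commit to a pooled choice.

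Finally, log-normal is not the inferior method throughout. If gabapentin lowers doses among users, it has more power than a ratio of means. Baseline opioid adjustment is a matter of precision, since randomisation does not require it.

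**Conclusion.** The point holds as an open choice that should be closed; it is not an error already built into the results. For pain, the scale should follow the hypothesis and the sample size, both in points. Moving to logs of positive scores would cut power from about 82% to about 55%, if scores behave like a rounded and clipped normal with the plan's mean and SD.

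For opioid dose, the scale determines which mechanism can be detected. Logs of positive doses have no power beyond the 5% error rate if the whole fall comes from more non-users, but they do better if users take less. It would be tempting to conclude that log-normal is what would make Hypothesis 1.2 fail. That goes too far: the zero-keeping ratio of means detects the effect in only 18-19% of trials in the 20% versus 36% case, and power is low on every scale unless variability is small. The zero shares and log-SDs are assumptions throughout.

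Type I error exceeds 5% only if the scale is chosen by arm or by result.

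**What to change.** Before the interim analysis, amend Section 10.0 as follows.

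- **VHNSS pain:** mean difference in points on the raw 0-10 scale, with robust standard errors.
- **Opioid dose:** ratio of mean doses from a model that keeps zeros, for example log-link quasi-Poisson with robust variance and a small-sample correction. Name log-normal on positive doses as a sensitivity analysis. A two-part model would be a reasonable alternative if its overall contrast is defined in advance.
- **Covariate for Hypothesis 1.2:** add baseline opioid dose, derived in morphine equivalents from the baseline pain-medication record, and say how a baseline of zero enters the model.
- **Distribution checks:** on pooled data only, by someone without the arm codes. The plan describes no masking of treatment, so this has to be stated.

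The cost is wording plus conversion of the baseline medication record; sample size and visits do not change. The price is some loss of power, at any share of zeros, if the true effect is a proportional dose reduction among users. At log-SD 0.8 with 10% zeros per arm, that is 24% against 29-30%. The change does not make Hypothesis 1.2 well powered, and the plan should say so.
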